#### **9.2.4. Criteria for Assessing Efficacy**

Efficacy measurements in this study will be based on changes from baseline in TEWL and Corneometer values at each visit. The baseline for these measurements will be defined as the measurements made 60±15 minutes after the facial peel procedure, before any test product application. Differences between product groups will also be explored.

#### **9.2.5. Criteria for Assessing Local Tolerance**

Secondary assessments of local tolerance will be based on Dermatologist and Subject self-assessment scores at each visit and reported adverse events. The baseline for these assessments will be defined as the assessments made 60±15 minutes after the facial peel procedure, before any test product application.

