## 2. OBJECTIVE(S) AND ENDPOINT(S)

Objective(s)	Endpoint(s)
Primary	
Assessment of the local tolerance of the test product in subjects who have undergone a 70% Glycolic Acid facial peel	Evaluator (Dermatologist) global assessment of tolerance
Secondary	
Assessment of skin recovery (change from baseline) over a period of 14 days in subjects who have undergone a 70% Glycolic Acid facial peel	Combined (sum of) Evaluator (Dermatologist) scores for signs/symptoms of erythema, edema, desquamation and dryness  Individual Evaluator (Dermatologist) scores for erythema, edema, desquamation and dryness  Combined (sum of) subject self-assessment scores for redness, pain, stinging/burning, itching, tightness and dryness  Individual subject self-assessment scores for redness, pain, stinging/burning, itching, tightness and dryness  Instrumental measurement of barrier function (Tewameter) and moisturisation (Corneometer)  Subject global self-assessment
Assessment of skin recovery (change from baseline) between treatment groups.	All assessments and measurements listed above

Document Name	Protocol 206827 CCI doc	Document Identifier	Effective Date
Type	Version		
eldo controlled	4.0; Most-Recent; Effective; CURRENT	090032d580d98eb9	15-Sep-2017 09:27:15

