Document Name	Protocol 206827 CCI doc		
Type	Version	Document Identifier	Effective Date
eldo controlled	4.0; Most-Recent; Effective; CURRENT	090032d580d98eb9	15-Sep-2017 09:27:15
Reason For Issue	Auto Issue		

the cutaneous damage for both groups, making it more difficult to measure a cosmetic benefit over time. Barrier function was observed to gradually worsen over the duration of the study, with weak indications of improvement between days 4 and 7. There was no statistically significant barrier function benefit between groups at any time point.

Based on this literature review, subject visits have been included at 24-72 hours post-procedure, where differences between control and test groups are expected to be largest. While it is expected the skin's barrier function will return to normal 24 to 48 hours following the procedure, the total duration of the test phase is 14 days to enable sufficient time to monitor desquamation and erythema compared to the post-procedure, pre-treatment baseline.

Document Name	Protocol 206827 CCI doc		
Type	Version	Document Identifier	Effective Date
elido controlled	4.0; Most-Recent; Effective; CURRENT	090032d580d98eb9	15-Sep-2017 09:27:15
Reason For Issue	Auto Issue		

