### 6.3.10. Instrumental Measurements Pre-Procedure

Instrumental measurements of Transepidermal Water Loss and skin hydration will be conducted by the Investigator or designee and recorded on the eCRF. Subjects will acclimatize to the controlled room temperature ( $21\pm1$  °C) and humidity ( $50\pm10\%$ ) for at least 30 minutes prior to instrumental assessment.

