### 6.3.13. Dermatologist Assessment Pre-Procedure

The following assessments will be conducted by a dermatologist reflective of the subject's facial skin condition at the time of the evaluation and recorded on the eCRF. Whenever possible, it is preferable for the same dermatologist to evaluate the same subject through the entire study.

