### 9.3.3. Secondary Analysis(es)

Changes from baseline in the Evaluator, Subject self-assessment and instrumental endpoints will be tabulated by product group and summarized descriptively using means, standard deviations and 95% confidence intervals and assessed for significance (different from zero) using t-tests or Wilcoxon signed rank tests dependent upon the distribution of the data.

Differences between product groups in the mean changes from baseline in Evaluator, Subject self-assessment and instrumental endpoints will also be explored using t-tests or Wilcoxon rank sum tests and summarised using 95% confidence intervals.

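### Skin recovery is tested only as change from 60 minutes after the peel, so for TEWL and Corneometer the plan cannot show whether skin is back at its recorded pre-peel level

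*Protocol*

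**What the plan says.** Section 2 gives the secondary objective as "Assessment of skin recovery (change from baseline) over a period of 14 days", followed by a second objective that compares this recovery between groups. Section 9.2.4 sets the reference for TEWL and Corneometer: "The baseline for these measurements will be defined as the measurements made 60±15 minutes after the facial peel procedure". Section 9.2.5 does the same for the scores: "The baseline for these assessments will be defined as the assessments made 60±15 minutes after the facial peel procedure". In both cases this is before any test product is applied. Section 9.3.3 then plans: "Changes from baseline in the Evaluator, Subject self-assessment and instrumental endpoints will be tabulated by product group". Each change is tested against zero with a t-test or signed rank test, and the groups are compared with unadjusted t-tests or rank sum tests.

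The same measures are also taken before the peel at Visit 3. Section 6.3.10 says: "Instrumental measurements of Transepidermal Water Loss and skin hydration will be conducted by the Investigator or designee and recorded on the eCRF". Section 6.3.12 collects six subject symptoms. Section 6.3.13 collects four dermatologist signs, scored "reflective of the subject's facial skin condition at the time of the evaluation". Sections 9.2.4, 9.2.5 and 9.3.3 give these values no role.

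Section 3.4 explains the choice. The 14-day phase is meant to follow desquamation and erythema against the post-peel, pre-treatment value. The same sentence expects barrier function to be normal again 24 to 48 hours after the procedure.

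**The concern.** Recovery normally means movement back towards the state before the injury. A change measured from the injured state shows that something has moved, but not how far it still has to go. The protocol's own review of a cited peel study notes that natural repair reduces the damage in both groups. A within-group change that differs from zero is therefore weak evidence about recovery.

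The within-group TEWL change is also the quantity on which Section 9.1 bases the sample size, so it is likely to be quoted when results are reported. If it is read as recovery of the barrier, the plan has no figure to support or contradict that reading. The 24 to 48 hour expectation in Section 3.4 cannot be checked by any planned analysis.

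A second, weaker question concerns signs that may appear late. If desquamation and evaluator-graded dryness are near 0 at 60 minutes, change from that point leaves little room to show improvement.

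**Working it through.** **1. The plan's own figure.** Section 9.1 gives 40 per group, a within-group TEWL change of 1.83, SD 4.053, two-sided alpha 0.05 and 80% power. For a one-sample t-test on the change, the noncentrality is 1.83 × √40 / 4.053 = 2.86. Power is 79.5% (81.5% by normal approximation), and the change detectable at exactly 80% is 1.84. The figure reproduces. By Section 9.2.4 it refers to change from the 60-minute value.

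**2. What that change can show.** Let P be the pre-peel value, B the 60-minute value and T the value at a visit. Then

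T − P = (T − B) + (B − P).

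The plan estimates T − B. Return to the pre-peel level concerns T − P, which needs P. If the peel raises mean TEWL by D and a fraction f of the rise remains, then T − B = −(1 − f)D and T − P = fD. The documents do not give D or f, so the values below are assumptions. SD 4.053 and n = 40 are from Section 9.1.

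| D | f | T − B | Power of planned test | Still above pre-peel |
|---|---|---|---|---|
| 4 | 0 | −4 | about 100% | 0 |
| 4 | 0.25 | −3 | 99.5% | 1 |
| 4 | 0.5 | −2 | 86% | 2 |
| 6 | 0.5 | −3 | 99.5% | 3 |
| 10 | 0.5 | −5 | about 100% | 5 |

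The second and fourth rows have the same planned result, −3, but differ threefold in what remains. A rise of 2 that resolves fully gives −(1 − 0) × 2 = −2, the same as a rise of 4 that is only half resolved. The planned analysis cannot separate such cases. The algebra is the same for Corneometer. Section 6.3.14 lets acid contact vary from 1 to 3 minutes by subject, so B − P may well differ between subjects.

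**3. The 0-3 scores.** Here 0 is labelled as absence of the sign, so a raw visit score has a fixed meaning. The possible problem is the floor. If a share q of subjects score 0 at 60 minutes, at most 1 − q can improve. With q assumed at 50%, 70%, 90% or 100%, that is 50%, 30%, 10% or 0%. The protocol gives no 60-minute data from which to choose q.

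The only time course it cites is a study of a 5% retinoic acid peel. In that study desquamation differed between groups on Days 4 to 7, and "Barrier function was observed to gradually worsen over the duration of the study". The first of these dates a group difference, not the onset of peeling.

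**4. The combined score.** Suppose erythema goes from 2 to 0 and desquamation from 0 to 2 (assumed). The combined change is (0 − 2) + (2 − 0) = 0. The individual scores are listed as endpoints beside the sum, and their tables would show −2 and +2.

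**5. The group comparison.** P and B both precede product use. Under randomisation B − P has the same expectation in both groups, so the expected group difference in T − B equals that in T − P. The reference is valid here. The unadjusted comparison may lose precision. With equal variances and correlation ρ between B and T, a change score has variance 2σ²(1 − ρ), while adjustment for B leaves σ²(1 − ρ²). The ratio, (1 + ρ)/2, is below 1 for any ρ < 1.

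**The case against.** The strongest reply is that the baseline is deliberate and consistent. Section 2 itself defines recovery as change from baseline, Section 3.4 gives the reason, and no endpoint promises return to the pre-peel state. That stands as a defence of the choice and of the between-group use. It does not supply the reading that Section 3.4 relies on when it expects barrier function to normalise.

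A reader might infer that the baseline falls before peeling and dryness can develop, so that these items can only worsen. The documents do not support this. The cited time course is for a different acid, and subjects may feel dryness or tightness within the hour. A floor can be inferred as possible, but it is not established.

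A reader might also infer that the combined score hides opposite trends. It does not, because the individual scores are reported as well. For the 0-3 items, 0 is an absolute anchor and Section 9.2.5 refers to scores at each visit. Where the pre-peel score is 0, a difference from pre-peel adds nothing to the raw score.

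Nor are the pre-peel values unused everywhere. The dermatologist's global tolerance rating (Section 6.8.10) may draw on all of a subject's data, although that is a tolerance rating, not a recovery analysis.

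Finally, extra tables are commonly left to the SAP, which is not available here and may contain them. The reference point and the tests, however, are fixed in the protocol.

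**Conclusion.** The point holds in a limited form. For TEWL and Corneometer, the planned within-group test can be significant while skin is well short of its pre-peel level, and no planned analysis would show the shortfall. Under the assumed rises of 4 to 10 units with half remaining, power is 86% or more with 2 to 5 units still unrecovered. These sizes depend on the assumed D and f and on the SD of 4.053. The inability to distinguish full from partial recovery does not depend on them.

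For desquamation and evaluator-graded dryness, a floor at 60 minutes is possible but is an inference. It would be wrong to say that the recovery objective cannot be answered at all, or that the 60-minute baseline is an error: it is valid for comparing the groups. The primary endpoint and the success criterion in Section 9.2.3 are unaffected.

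**What to change.** - **Sections 9.2.4 and 9.3.3, TEWL and Corneometer.** Add the difference from the pre-procedure value at each post-treatment time point, by group, with 95% confidence intervals, and use it as the description of recovery. Read the interval rather than a test against zero, since a non-significant difference would not prove return.
- **Sections 9.2.5 and 9.3.3, 0-3 items.** Add raw scores by visit, or the proportion of subjects back to their pre-procedure score.
- **Section 9.3.3, between groups.** Keep the 60-minute baseline. Replace the unadjusted t-test on change with a model adjusted for the 60-minute and pre-procedure values where the distribution allows, and keep the rank sum test otherwise.

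No new data or visits are needed. The cost is a changed model for the between-group comparison and more secondary tables. Per group there are 2 instrumental measures at 7 time points (14 differences) and 10 individual items at 6 time points (60 rows of scores or proportions).

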#### **9.2.6. Handling of Dropouts and Missing Data**

Missing data will not be imputed. All data available for dropouts will be considered in analyses.

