## SCHEDULE OF EVENTS

Procedure/ Assessment	Visit 1 Day 1	Visit 2 Day 2	Visit 3  Day 8	Visit 4  Day 9	Visit 5  Day 10	Visit 6  Day 11	Visit 7  Day 15	Visit 8  Day 22
	Screening/ Washout	1 Day After Visit 1	6 Days after Visit 2, Day of Procedure	1 Day after Visit 3	1 Day after Visit 4	1 Day after Visit 5	4 Days after Visit 6	7 Days after Visit 7
Informed Consent	X							
Demographics	X							
Medical History	X							
Current / Concomitant Medication	X	X	X	X	X	X	X	X
Adverse Events		X	X	X	X	X	X	X
Continued Subject Eligibility		X	X	X	X	X	X	X
Compliance (Diary review) 		X	X	X	X	X	X	X
Fitzpatrick Skin Type Assessment (Appendix 2)	X							
Glogau Photoaging Type Assessment (Appendix 3)	X							
In/Exclusion Criteria	X 	X 	X 					
Subject Eligibility	X							
Study Material Sensitivity Test	X 							
Subject Self-Assessment Sensitivity	X 	X 	X 					
Dermatologist Assessment Sensitivity	X 	X 	X 					
Exclusion Criteria 9	X	X	X					
Subject Eligibility	X	X	X					
Subject Randomisation			X					
Instrumental Measurements Pre-Procedure			X					
Image capture (VISIA) Pre-Procedure			X					
Subject Self-Assessment Pre-Procedure			X					
Dermatologist Assessment Pre-Procedure			X					
Dermatological Procedure (Facial Peel)			X 					
Dermatologist Assessment Post-Procedure, Pre-Treatment (BASELINE)				X 				
Instrumental Measurements Post- Procedure, Pre-Treatment (BASELINE)				X 				
Image capture (VISIA) Post-Procedure, Pre-Treatment (BASELINE)				X 				
Subject Self-Assessment Post-Procedure, Pre-Treatment (BASELINE)				X 				
Washout Products and Washout Diary Dispensing	X							
Test Product and Test Diary Dispensing, Washout Diary return.				X 				
Supervised Test-Product Application Post- Procedure				X 				
Instrumental Measurements Post- Procedure, Post-Treatment 			X	X	X	X	X	X
Image capture (VISIA) Post-Procedure, Post-Treatment 				X				X
Subject Self-Assessment Post-Procedure, Post-Treatment 			X	X	X	X	X	X
Subject Global Self-Assessment								X
Dermatologist Assessment Post-Procedure, Post-Treatment 			X	X	X	X	X	X
Dermatologist Global Assessment of Tolerance								X

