### 4.4. Withdrawal/ Stopping Criteria

A subject may withdraw from the study at any time at his/her own request, or may be withdrawn at any time at the discretion of the investigator for safety, behavioural or administrative reasons.

If the reason for removal of a subject from the study is an AE or an abnormal laboratory test result, the principal specific event or test will be recorded on the electronic Case Report Form (eCRF). If a subject is withdrawn from the study because of a product limiting AE, thorough efforts should be clearly made to document the outcome. Any AEs ongoing at the final visit will be followed up until resolved, the condition stabilizes, is otherwise explained, or the subject is lost to follow-up.

The following actions must be taken in relation to a subject who fails to attend the clinic for a required study visit:

- The site must attempt to contact the subject and re-schedule the missed visit as soon as possible.

Document Name	Protocol 206827 CCI doc		
Type	Version	Document Identifier	Effective Date
elido controlled	4.0; Most-Recent; Effective; CURRENT	090032d580d98eb9	15-Sep-2017 09:27:15
Reason For Issue	Auto Issue		

- The site must counsel the subject on the importance of maintaining the assigned visit schedule and ascertain whether or not the subject wishes to and/or should continue in the study.
- In cases where the subject is deemed 'lost to follow up', the investigator or designee must make every effort to regain contact with the subject (where possible, at least 2 telephone calls). The contact attempt should be documented in the subject's record.
- Should the subject continue to be unreachable, only then will he/she be considered to have withdrawn from the study with a primary reason of "Lost to Follow-up".

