### 5.4. Product Compliance

A daily dairy will be used to monitor and promote compliance. Subjects will not be excluded due to missed applications, but will be reminded to use the products as per the instructions provided and to complete the diary card on a daily basis to encourage compliance. Missed or additional product applications will be recorded by the

Document Name	Protocol 206827 CCI doc		
Type	Version	Document Identifier	Effective Date
eldo controlled	4.0; Most-Recent; Effective; CURRENT	090032d580d98eb9	15-Sep-2017 09:27:15
Reason For Issue	Auto Issue		

Investigator or designee as deviations. Subjects will be asked to bring their washout and test products to each site visit.

To be considered compliant and part of the per-protocol (PP) population, a subject must have used the test product and/or sunscreen at least 80% of the instructed number of applications following completion of the facial peel procedure.

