Subjects will be instructed to contact the study site (in person or by phone) in case of discomfort between visits. A medically qualified dermatologist will evaluate the subject's reports of discomfort and determine an appropriate course of action, including whether to discontinue a subject's involvement in the study. Adverse events will be reported as per the procedures in Section 7.

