### **6.8.10. Dermatologist Global Assessment**

The Dermatologist will assess the local tolerance of the post-procedure skin care regimen in context of the expected effects of the procedure for each subject using the scale below and document the score on the eCRF. To make this assessment, the Dermatologist will draw on the total set of clinical and subject self-assessment data for each subject. The Dermatologist must be unaware of whether a subject was randomized to test product to protect the blind.

Document Name	Protocol 206827 CCI doc		
Type	Version	Document Identifier	Effective Date
elido controlled	4.0; Most-Recent; Effective; CURRENT	090032d580d98eb9	15-Sep-2017 09:27:15
Reason For Issue	Auto Issue		

Rating	Description
0 - Product Regimen was Well Tolerated	No clinically significant worsening of the expected signs/symptoms of the procedure. No new signs/symptoms manifest during product use.
1 - Product Regimen was Not Well Tolerated	Clear, clinically relevant worsening of the severity or frequency of expected signs/symptoms of the procedure and/or any occurrence of new, unexpected signs/symptoms during product use.

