### 6.8.12. Discharge from Study

Subjects will be evaluated to determine if they completed all study procedures or if they were discontinued from the study early. If the subject discontinued at any point during the study, the primary reason for withdrawal should be recorded on the Study Conclusion page of the eCRF by selecting one of the options below.

1. Subject did not meet study criteria
2. Adverse Event
3. Lost to Follow Up
4. Protocol Violation
5. Withdrawal of Consent
6. Other

Document Name	Protocol 206827 CCI doc		
Type	Version	Document Identifier	Effective Date
elido controlled	4.0; Most-Recent; Effective; CURRENT	090032d580d98eb9	15-Sep-2017 09:27:15
Reason For Issue	Auto Issue		

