### 9.2. General Considerations

#### 9.2.1. Definition of Analysis Populations

All randomized subjects will be included in the intent-to-treat (ITT) population. All subjects with at least one application of product in the test phase (i.e. test product for subjects in Group I or sunscreen for subjects in Group II) will be included in the Safety population.

Document Name	Protocol 206827 CCI doc		
Type	Version	Document Identifier	Effective Date
elido controlled	4.0; Most-Recent; Effective; CURRENT	090032d580d98eb9	15-Sep-2017 09:27:15
Reason For Issue	Auto Issue		

Subjects will be considered eligible for a Per Protocol (PP) population if they were randomized, received at least one application of test product, had at least one post-procedure, post-treatment assessment available and were compliant with both test and washout products post-procedure. Other considerations for eligibility for the PP population including but not limited to use of concomitant medications will be detailed in the Statistical Analysis Plan prior to database unblinding.

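### The primary tolerance rating is made only at Visit 8 and is not required at early discontinuation, so women who leave for local intolerance ordinarily drop out of the primary proportion

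*Protocol*

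**What the plan says.** Protocol section 2 names the evaluator's global assessment of tolerance as the primary endpoint. In the Schedule of Events the row "Dermatologist Global Assessment of Tolerance" is marked for Visit 8 only, and the visit lists in section 3.1 place it at Visit 8 alone. Section 6.8.10 gives the two-level scale (0 well tolerated, 1 not well tolerated) and its basis: "the Dermatologist will draw on the total set of clinical and subject self-assessment data for each subject".

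Early departure is dealt with in three places:

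- Section 6.3.14: after a report of discomfort a dermatologist is to "determine an appropriate course of action, including whether to discontinue" the subject's involvement.
- Section 4.4: "If a subject is withdrawn from the study because of a product limiting AE", efforts must be made to document the outcome of the event.
- Section 6.8.12: "the primary reason for withdrawal should be recorded on the Study Conclusion page of the eCRF".

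None of the three asks for the global rating, and no early-termination visit is described. Section 4.5 allows no replacement after randomisation.

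On analysis, section 9.2.6 says: "Missing data will not be imputed. All data available for dropouts will be considered in analyses". Section 9.2.3 declares success if more than 50% of test-product subjects have a favourable rating. Section 9.3.2 summarises the favourable proportion in each group with a 95% confidence interval.

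**The concern.** In a tolerance trial, the event that makes a woman a primary failure can also be the event that removes her before she is rated. A woman withdrawn on Day 10 with a new, unexpected skin reaction meets the section 6.8.10 description of a regimen not well tolerated, yet as written nobody has to record that score. Another may leave because of ordinary peel effects and deserve a 0. The withdrawal reason alone cannot separate the two; a blinded rating can.

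Missingness is therefore linked to the outcome, and with observed ratings only the error favours the product. At stake are the reported proportion, its confidence interval and any between-group comparison built on it. Analysis rules written later cannot fix this, because the gap is in what is collected.

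The concern is limited to women who leave the study. Under section 5.4, "Subjects will not be excluded due to missed applications", so a woman who stops applying the product but keeps attending is still rated at Visit 8.

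**Working it through.** **The plan's own figure.** Section 9.1 expects 80 completers of 100 randomised, 40 per group. That is 20% non-completion: 100 × (1 − 0.20) = 80. The power statement in the same section concerns the secondary TEWL endpoint and has no bearing here.

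**Inputs**

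- Test group: 50 randomised, 40 rated, 10 not rated. This assumes 1:1 allocation; the ratio is not stated, but 40 completers per group are.
- k, the number of those 10 who leave for local intolerance. The protocol gives no figure, so k = 1 or 2 is an assumption. Section 3.4 offers two benchmarks. The one-week retinoic acid peel study lost 1 of 26 test-group subjects to contact dermatitis: 50 × 1/26 = 1.9 per 50. The pulsed-laser study had one withdrawal within 14 days (Day 7): 50 × 1/74 = 0.7 per 50. Its other withdrawal came at the 28-day visit, outside this trial's 14-day test phase, and is not counted.
- x, favourable ratings among the 40. x = 36 is an illustration.

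**Comparison A: add only the intolerance withdrawals, as not favourable.** Rated-only x/40 against x/(40 + k), with exact 95% intervals:

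| Calculation | Favourable | 95% CI |
|---|---|---|
| 36/40, rated only | 90.0% | 76.3–97.2 |
| 36/41, k = 1 | 87.8% | 73.8–95.9 |
| 36/42, k = 2 | 85.7% | 71.5–94.6 |

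The largest possible inflation is at x = 40: 40/40 − 40/41 = 2.4 points for k = 1, and 40/40 − 40/42 = 4.8 points for k = 2.

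**Comparison B: rate all 10 dropouts, as the fix below would.** Let f be the favourable share among those leaving for other reasons. The proportion is (36 + f(10 − k))/50.

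- k = 2, f = 100%: (36 + 8)/50 = 88.0%.
- k = 2, f = 90%: (36 + 7.2)/50 = 86.4%.
- k = 1, f = 100%: (36 + 9)/50 = 90.0%.
- k = 1, f = 90%: (36 + 8.1)/50 = 88.2%.

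Against the rated-only 90.0%, the shift is 2.0 to 3.6 points with two intolerance withdrawals and 0 to 1.8 points with one.

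**Success rule, on comparison A.** The verdict changes when x/40 > 0.5 but x/(40 + k) ≤ 0.5. For k = 1 there is no such x (21/41 = 51.2%). For k = 2 only x = 21 qualifies (52.5% against 21/42 = 50.0%).

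**Worst-case bound.** Counting all 10 unrated women as not favourable gives 36/50 = 72.0% (57.5–83.8). The success verdict would then differ from rated-only for x = 21 to 25.

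**The case against.** The strongest reply is that most of this is either analysis detail for the SAP or too small to matter. Several parts of it stand.

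- **The denominator belongs to the SAP.** Sections 9.2.3 and 9.3.2 name no denominator, and section 9.3 defers detail to a SAP that is not at hand. That silence is not a finding. The collection gap is, because the SAP cannot create ratings.
- **All randomised women might seem to count, with the unrated as failures.** A reader might infer this from section 9.2.1, "All randomized subjects will be included in the intent-to-treat (ITT) population", and so claim an 18-point overstatement (90.0% against 72.0%). The documents do not support it. Section 9.2.1 defines who belongs to the population, not how a missing rating is scored. Scoring it as a failure would be a form of imputation, which section 9.2.6 rules out. The text points to observed ratings, and 72.0% is only a bound.
- **A rating for dropouts is not forbidden.** Section 6.8.10 speaks of each subject and rests the score on accumulated data, so an evaluator could rate someone who left. But the instruction sits under Visit 8 and the schedule confines it there. Feasible is not the same as required.
- **Intolerance remains visible.** A reader might infer that the plan conceals it. It does not: sections 4.4 and 6.8.12 record the event and the reason for leaving, section 9.2.5 uses visit scores as tolerance assessments, and section 9.3.4 tabulates adverse events by group.
- **Early ratings carry their own bias.** A woman who leaves after a day or two for unrelated reasons may score 0 simply because little has happened yet. This is a real drawback of the fix, and it is why early ratings should be identifiable.

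**Conclusion.** The point holds in limited form and should be fixed. As written, women who leave for local intolerance would ordinarily be missing from the primary proportion, which biases it toward well tolerated.

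Under the stated assumptions the overstatement is at most 2.4 points with one intolerance withdrawal and 4.8 with two when only those women are added. In the 36/40 example it is between 0 and 3.6 points if every dropout were rated. The size depends on the assumed number of intolerance withdrawals and on how the other dropouts would have been rated; the protocol gives neither.

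It would be wrong to conclude that the success criterion is unsafe in general. With high tolerance the verdict does not move, and in comparison A it changes at a single value. The analysis is descriptive, and what is affected is the headline figure and its interval.

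**What to change.** **Collection.** In the Schedule of Events and sections 6.8.10 and 6.8.12, require the blinded evaluator to complete the global rating at early discontinuation, in both groups, for every randomised subject who started the post-peel regimen. Use the data then available and the existing section 6.8.10 definitions, and record the day of rating.

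**Analysis.** In sections 9.2.6 and 9.3.2, allow one labelled sensitivity analysis that counts any subject still unrated as not favourable, stated as an exception to the no-imputation rule. Report the primary proportion with and without early ratings.

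Investigator-judged relatedness to product (section 7.3) should not define a primary failure, because section 5.8.2 lets some investigators and designees be unblinded.

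**Cost.** Wording in five places, and about 10 extra ratings per group on the protocol's own figures (50 − 40). No new staff, procedure or change to withdrawal rules is needed, and the withdrawal reason is already on the eCRF. The downsides are that early ratings rest on shorter follow-up and may lean favourable for women who leave soon for unrelated reasons, and that the headline proportion may be slightly lower.
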